### **10.3.2. Treatment Group Comparability**

#### **10.3.2.1. Study Participant Disposition**

Intention-to-treat population will be used for this analysis. All study participants who discontinue the study will be identified, and the extent of their participation in the study will be reported. If known, a reason for their discontinuation will be given. The primary reasons for discontinuation will be listed and will be summarized by treatment. The discontinuation due to AE will be summarized by adverse event and treatment. The percentage of study participants discontinuing from each treatment will be compared using the Fisher's exact test.

#### **10.3.2.2. Study Participant Characteristics**

Intention-to-treat population will be used for this analysis. Demographic and baseline characteristics will be summarized by treatment group. Categorical variables will be summarized by frequencies and percentages. For categorical variables, comparisons between treatment groups will be assessed using a Pearson chi-square test. Continuous variables will be summarized by mean and SD. For continuous variables, comparisons between the treatment groups will be performed using a 1-way analysis of variance with treatment as the fixed effect.

#### **10.3.2.3. Concomitant Therapy**

Intention-to-treat population will be used for this analysis. Listings and summary of concomitant therapies will be provided by treatment group.

#### **10.3.2.4. Treatment Compliance**

Treatment compliance will be listed using all randomized study participants and summarized using the modified intention-to-treat population. For a given study participant, overall compliance for treatment period is defined as, not missing 2 or more consecutive doses of the assigned treatment, or, missing 4 or more at any point in the study. Study participants who miss 4 or more doses at any point during the study will not be included in the efficacy analysis.

Adherence to the dosing algorithm is required from Visit 3 (Randomization) up to Visit 21 (Week 32, inclusive), although the last scheduled opportunity for dose adjustment will occur at Week 31. Adherence to the dosing algorithm will be assessed based on the number and percentage of investigator-reported prescribed doses that do not follow the investigator-calculated algorithm dose, which represent intentional deviation from the algorithm, and the number and percentage of investigator-calculated doses that are not equal to the sponsor-calculated algorithm doses.

### **10.3.3. Efficacy Analyses**

#### **10.3.3.1. Primary Analyses**

The primary efficacy outcome is HbA1c change from baseline to Week 32 for LY arms. The mixed-effect model repeated measures (MMRM) with BMI strata, treatment, visit, SU (Y/N), and treatment-by-visit interaction as fixed effects, HbA1c baseline as a covariate will be used for the analysis. The within-study participant correlation will be modelled through a variance-covariance structure. The dependent variable will be the post-baseline change from baseline values. The unstructured covariance matrix will be selected initially. There will be no explicit missing data imputation as the missing values are handled implicitly by the MMRM model.

#### **10.3.3.2. Secondary Analyses**

The secondary analysis will be performed on the efficacy analysis set. The main secondary efficacy analysis aims to compare LY versus Insulin Degludec with regarding to HbA1c change from baseline at Week 12 and 32. The estimand of interest is the treatment differences in HbA1c at 12 and 32 weeks while the study participants are on study treatment. The efficacy analysis set (EAS) will be used to calculate the mean difference between treatments. Similar MMRM model will be used for the main secondary analysis. The least-squares (LS) mean differences and the standard errors from each imputed sample will be calculated based on the above model, and the final estimation for the means, standard errors, 90% confidence intervals, and p-values will be reported.

A supplementary analysis will be conducted to evaluate the “treatment policy” estimand, which is defined as the treatment differences in HbA1c at 32 weeks with the randomized treatment based on FAS. The estimator is defined as the mean difference between treatments based on FAS. The missing values will be imputed using multiple imputations. The similar MMRM model will be performed on imputed data and inferences will be drawn based on the framework of multiple imputations (Rubin, 1987).

In addition to the main secondary efficacy analysis of HbA1c, the following secondary efficacy outcomes will be analyzed:

- Body weight and change from baseline to 12 and 32 weeks
- Fasting blood glucose and change from baseline at 12 and 32 weeks

The analyses of the HbA1c change, mean weight change, fasting blood glucose change and SMBG change from baseline will be conducted through MMRM similar to that of the primary efficacy outcome. The corresponding baseline will be used in the model instead of the baseline HbA1c levels. The MMRM model will also include a term for the HbA1c stratification group. The treatment p-value will be used as evidence of difference between LY3209590 and insulin degludec, while the comparison of LS means versus insulin degludec (unadjusted for multiple comparisons) and its 90% confidence interval will provide magnitude and significance of this difference.

### 10.3.3.3. Exploratory Analyses

LY3209590 concentration data will be analyzed using standard nonlinear mixed-effects modeling implemented on the NONMEM software. The relationships between LY3209590 dose and/or concentration and efficacy, tolerability, and safety endpoints will be characterized, such as fasting glucose, SMBG, HbA1c, hypoglycemia, body weight, blood pressure, pulse rate, and corrected QT interval (QTc).

Additionally, the impact of intrinsic and extrinsic study participant factors such as age, weight, gender and renal function on PK and/or PD parameters may be examined as needed. If ADA titers are detected from immunogenicity testing, then the impact of immunogenicity titers on LY3209590 PK or any relevant PD parameters will also be examined.

### 10.3.4. Safety Analyses

The FAS will be used for safety analyses. Both the overall and the pairwise comparisons of each LY3209590 arm versus insulin degludec will be reported for these safety analyses.

Safety measures include liver biomarkers (ALT), hypoglycemia, vital signs (BP and pulse rate), body weight, TEAEs (including SAEs and AEs of special interest), laboratory measures (including anti-LY3209590 antibodies), and ECGs. Summary statistics will be presented by treatment for the safety measures.

The summary statistics for continuous variables will be sample size, mean, SD, median, minimum, and maximum.

The summary statistics for categorical variables will be sample size, frequency, and percentage.

Exposure to each therapy during the treatment period of the study will be calculated for each study participant and summarized by treatment group.

In addition, the following safety outcomes will be analyzed on the efficacy analysis set population:

- ALT change from baseline to 12 and 32 weeks

The change from baseline of ALT will be analyzed using MMRM model. In addition, Bayesian model will be used to conduct the same analysis. The corresponding baseline will be used in the model instead of the baseline HbA1c levels. The MMRM model will also include a term for the HbA1c stratification group.

Additional analyses, such as concentration-safety laboratory plots, may be performed, if warranted upon review of the data.

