Study participants discontinuing from the IP study treatment prematurely for any reason should complete AE and other follow-up procedures per Section 2 (Schedule of Activities), Section 9.2 (Adverse Events), and Section 9.4 (Safety) of this protocol.

Study participants who stop the IP permanently may receive another glucose-lowering intervention, if appropriate, and will continue participating in the trial according to the protocol to collect all planned efficacy and safety measurements.

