## 10. Statistical Considerations

### 10.1. Sample Size Determination

Approximately 375 study participants will be randomized in a 1:1:1 ratio to LY3209590 in one of two dosing algorithms or insulin degludec treatment arms, assuming a 20% dropout rate resulting in approximately 300 total completers at 32 weeks (100 completers per treatment arm). The sample size was calculated based on the statistical power for the primary and liver safety endpoints.

- The 300 completers will provide 90% statistical power to demonstrate the noninferiority of the pooled LY3209590 arms versus insulin degludec for the change in HbA1c from baseline to 32 weeks (assuming non-inferiority margin is 0.4%, the SD is 1.1% and true mean difference is 0%) using two sided t-test at  $\alpha = 0.1$ .

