### 10.3. Statistical Analyses

#### 10.3.1. General Statistical Considerations

Statistical analysis of this study will be the responsibility of Lilly or its designee. Any change to the statistical methods described in the protocol will require an amendment only if it changes a principal feature of the protocol. Any other change to the statistical analyses and the justification for the change will be described in the statistical analysis plan (SAP) and/or clinical study report. Additional exploratory analyses of the data may be performed as deemed appropriate. Analyses will be fully detailed in the SAP.

Statistical analyses (including the primary analysis) will be conducted on the efficacy analysis set population. Safety analyses will be performed on the full analysis set.

No adjustments for multiplicity will be performed.

All tests of treatment effects will be conducted at a two-sided alpha level of 0.1 and/or two-sided 90% confidence interval, unless otherwise stated.

The baseline value used for the analyses will be the last scheduled baseline value obtained for each study participant prior to randomization. ALT, AST, and GGT will be average of 3 assessments as baseline.

The analysis of the main secondary efficacy endpoint and possibly other Bayesian analyses may be computed using Fixed and Adaptive Clinical Trial Simulator software. Remaining summaries and analyses will be performed using the SAS System.

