4.10. Safety Analyses

Safety measures will include AEs, vital signs, treatment exposure, adjudicated cardiovascular events, laboratory measures, and antibodies to LY3209590. Safety analysis will be reported for Safety Population and data measured while on treatment and after study drug discontinuation will be included.

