4.10.4.2. Liver Enzyme Elevation Measures

The liver enzymes and biomarkers (alanine aminotransferase [ALT], aspartate aminotransferase [AST], Alkaline phosphatase [ALP], total bilirubin[TBL], and Gamma glutamyl transferase [GGT]) measures will take log-transformation before performing the MMRM analysis. In addition, the percentage of patients with the following elevations in liver enzymes at any postbaseline visit after randomization including the treatment period and post-treatment follow-up period will be summarized for subsest based on baseline categories.

- The analysis of any postbaseline ALT (AST) ≥ 3 fold (3X) ULN will contain 4 baseline subsets:
 - patients whose non-missing maximum baseline value is less than or equal to 1X ULN,
 - patients whose maximum baseline is greater than 1X ULN but less than 3X ULN,
 - patients whose maximum baseline value is greater than or equal 3X ULN, and
 - patients whose baseline values are missing.
- The analysis of any postbaseline ALT (AST) ≥ 5 X ULN will be contain 5 baseline subsets:
 - patients whose non-missing maximum baseline value is less than or equal to 1X ULN,
 - patients whose maximum baseline is greater than 1X ULN but less than 3X ULN,
 - patients whose maximum baseline is greater than or equal to 3X ULN but less than 5X ULN,
 - patients whose maximum baseline value is greater than or equal to 5X ULN, and
 - patients whose baseline values are missing.
- The analysis of any postbaseline ALT(AST) ≥ 10 X ULN will contain 6 baseline subsets:

- patients whose non-missing maximum baseline value is less than or equal to 1X ULN,
 - patients whose maximum baseline is greater than 1X ULN but less than 3X ULN,
 - patients whose maximum baseline is greater than or equal to 3X ULN but less than 5X ULN,
 - patients whose maximum baseline is greater than or equal to 5X ULN but less than 10X ULN,
 - patients whose maximum baseline value is greater than or equal to 10X ULN, and
 - patients whose baseline values are missing.
- The analysis of any postbaseline TBL $\geq 2X$ ULN will contain 4 baseline subsets:
 - patients whose non-missing maximum baseline value is less than or equal to 1X ULN,
 - patients whose maximum baseline is greater than 1X ULN but less than 2X ULN,
 - patients whose maximum baseline value is greater than or equal to 2X ULN, and
 - patients whose baseline values are missing.

A listing of patients with any post randomization

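### The SAP drops the protocol's on-treatment ALT analysis without explanation, and its remaining ALT mean comparison does not say whether values after drug stop are included

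*Protocol*

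**What the plan says.** **Protocol.** Section 10.3.4 uses the FAS for safety and then adds: "In addition, the following safety outcomes will be analyzed on the efficacy analysis set population". ALT change to Weeks 12 and 32 is the only item in that list. It is to be analysed by MMRM with a term for the HbA1c stratum, and the same analysis is to be repeated with a Bayesian model. The efficacy analysis set (EAS, protocol 10.2 and SAP 4.1) drops data after rescue and data after study drug is stopped; the SAP sets the cut-off at last dose plus 10 days. On sizing, 10.1 states: "The sample size was calculated based on the statistical power for the primary and liver safety endpoints". The only calculation that follows is for HbA1c.

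**SAP.** Section 4.10 states: "Safety analysis will be reported for Safety Population and data measured while on treatment and after study drug discontinuation will be included". Section 4.1 gives the same rule. ALT is not among the EAS analyses in 4.8. In 4.10.4.2 the liver enzyme "measures will take log-transformation before performing the MMRM analysis". That MMRM is the generic laboratory model of 4.10.4: treatment, baseline, visit and visit-by-treatment, with compound symmetry and no HbA1c-stratum term. Section 4.10.4 limits it to the treatment period and scheduled visits. There is no Bayesian ALT model, and the list of main changes from SAP version 1 does not mention ALT.

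**Follow-up after drug stop.** Under protocol 8.1.1, participants who stop study drug permanently "will continue participating in the trial according to the protocol to collect all planned efficacy and safety measurements". The same section lists liver-test abnormality as a reason to stop.

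**The concern.** Protocol 3.3 names aminotransferase elevation as a risk suggested by preclinical data, in addition to the known insulin risks. Human exposure so far was up to 6 weeks; this trial runs for 32. The protocol singled out ALT for an on-treatment comparison, and that comparison has no counterpart in the SAP.

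What remains may mix on-drug and off-drug values in the LY3209590 arms. If ALT returns toward the comparator level after stopping, the estimated difference shrinks, which for a safety measure is the unfavourable direction. Participants who stop because of ALT are the ones whose later values would pull the mean down most.

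Protocol 10.3.1 and SAP 4.1 both say that a changed analysis and its justification will be described in the SAP and/or the clinical study report. The SAP gives no justification.

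**Working it through.** **1. The plan's own power figure.** Inputs from protocol 10.1 and 10.3.1: "The 300 completers will provide 90% statistical power to demonstrate the noninferiority of the pooled LY3209590 arms versus insulin degludec", "assuming non-inferiority margin is 0.4%, the SD is 1.1% and true mean difference is 0", two-sided alpha 0.1, and 100 completers per arm, so 200 pooled against 100.

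- SE = 1.1 x sqrt(1/200 + 1/100) = 1.1 x 0.1225 = 0.1347
- Power = Phi(0.4/0.1347 - 1.645) = Phi(1.324) = 90.7% (noncentral t: 90.6%)
- 300/(1 - 0.20) = 375

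The stated 90% and 375 reproduce on HbA1c alone. No liver figure can be checked, because neither document gives an ALT difference, SD, margin or power.

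**2. What that sample size detects for ALT.** At 90% power, the difference is (1.645 + 1.282) x 0.1225 = 0.358 SD. The documents give no log-scale SD. If it were 0.3 to 0.6 (assumed), this is exp(0.358 x 0.3) = 1.11 to exp(0.358 x 0.6) = 1.24, a rise of about 11% to 24%.

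**3. Which data enter the SAP's ALT model.**

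| Text | Points to |
|---|---|
| SAP 4.1 and 4.10, general safety rule | off-drug values included |
| SAP Table BDCM.1 footnote (hypoglycemia) and 4.11.1 (CGM) | explicit on-drug rules, with none for laboratory data |
| Protocol 5.1 and 5.1.1 | treatment period is 32 weeks |
| SAP 4.10.4 | MMRM limited to the treatment period, end not defined |
| SAP 4.10.1 | treatment-period exposure ends at drug discontinuation |

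Visit 801 follow-up values are outside the MMRM for participants who complete treatment. Off-drug values can enter only from participants who stop early and keep attending scheduled visits within the 32 weeks. They do not enter if the period ends at drug stop. The text leaves both readings open.

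**4. Size of the attenuation.** Let f be the share of LY3209590 values that are off drug and r the fraction of the effect reversed. On the log scale, the estimated ratio is exp((1 - f x r) x ln R). With an assumed R = 1.20 (ln R = 0.1823):

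| f | r = 1 | r = 0.5 |
|---|---|---|
| 0.10 | exp(0.90 x 0.1823) = 1.178 | exp(0.95 x 0.1823) = 1.189 |
| 0.20 | exp(0.80 x 0.1823) = 1.157 | exp(0.90 x 0.1823) = 1.178 |

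**5. Net effect on power.** Take the 0.358 SD effect, which has 90% power with 200 and 100 on-drug values. Adding off-drug values changes the effect to 0.358 x (1 - f x r) and the comparator n to 100/(1 - f), so power = Phi(effect/sqrt(1.5/n) - 1.645).

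- f = 0.05, r = 1: effect 0.340, n = 105.3, power 88.6%
- f = 0.20, r = 1: effect 0.287, n = 125, power 83.5%
- r = 0.5, f from 0.05 to 0.20: power stays at about 90%, because the added values offset the smaller effect

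**The case against.** The strongest reply is that SAP 4.10.4 already confines the MMRM to the treatment period. The same section describes the abnormal-value analysis as covering treatment and follow-up, and 4.10.1 ends treatment-period exposure at drug stop. Read that way, off-drug ALT is already excluded. This stands as a possible reading. A reader might infer that the SAP's ALT comparison definitely uses off-drug values, but the documents do not settle it.

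Second, all-data safety analysis is the protocol's own default (10.3.4), so the SAP's model is legitimate. That stands, and the model should be kept. It does not account for the omitted ALT exception.

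Third, the size rests on assumptions. The 20% in 10.1 is dropout, not participants off drug who still give blood, and 5.1.1 only encourages those who stop to remain. Washout of up to 10 weeks (7.8.1) would slow reversal. ALT change is exploratory, and no aminotransferase rise had been seen in people. All of this stands and limits the claim to modest attenuation.

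A reader might go further and infer that a liver signal could vanish. If 4% stopped at 8 times baseline and then normalised, exp(0.04 x ln 8) = 1.09 on drug would become 1.00 at Week 32. These figures are assumed. An on-drug MMRM would not return 1.09 either: those participants would have no Week 32 value, and the model would predict it from earlier visits. Rises of that size would also be expected to show in the categorical elevation tables and the listings of SAP 4.10.4.2, which do not depend on this choice.

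Finally, silence in the SAP is not in itself a breach, since the clinical study report may still carry the justification.

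**Conclusion.** The point holds in limited form. The protocol commits to an on-treatment ALT comparison at Weeks 12 and 32 by two methods; the SAP has neither and gives no reason. The one ALT mean model left can include values after drug stop, because its treatment period is not defined.

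The likely consequence is modest. An assumed ratio of 1.20 would be estimated as 1.18 to 1.16 with 10-20% off drug and full reversal, and closer to 1.20 with partial reversal. Power would fall from 90% to between 88.6% and 83.5% with 5-20% off drug and full reversal, and hardly at all with half reversal. The off-drug share, the reversal and the 1.20 are assumptions.

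The sizing sentence in 10.1 and the missing Bayesian specification are documentation points. A reader might infer from 10.1 that a power for liver safety has been stated, but none is printed, and the HbA1c calculation supports the sample size by itself.

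**What to change.** In SAP 4.10.4.2, add the protocol's on-drug log-ALT MMRM at Weeks 12 and 32 with the HbA1c-stratum term, next to the all-data model. Use the EAS cut-off for stopping study drug, but preferably keep values after rescue while study drug continues: the EAS as written drops them, although protocol 5.1.1 and 7.8.2.3 keep rescued participants on study drug. State the ALT baseline as well, since protocol 10.3.1 averages three assessments and SAP 4.10.4 takes the last nonmissing value.

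In SAP 4.10.4, state whether the treatment period ends at drug stop or at Week 32.

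Two wording changes: say that the Bayesian ALT analysis is withdrawn and why, or give its model and prior; and in protocol 10.1 remove the reference to liver safety, or give the ALT difference, SD and power behind it.

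The cost is one extra model run and a few sentences. The on-drug model relies on data being missing at random after drug stop, so it recovers only part of an effect in participants stopped for an ALT rise. That is a reason to report both models.

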#### 10.3.4.1. Adverse Events

Adverse Events will be listed by study participant, actual term, preferred term, severity, and relationship to the treatment. AEs will be summarized as TEAEs (defined as events that are newly reported after randomization or reported to worsen in severity from baseline). The incidence of study participants with at least 1 TEAE and the incidence of TEAEs by preferred term and system organ class will be presented by treatment group. The frequency and

percentage of TEAEs will be presented. The incidence of study participants with at least 1 TEAE assessed as possibly related to the investigational drug will be summarized by treatment group, in addition to the incidence of these possibly related TEAEs by preferred term. In addition, a summary of TEAEs by severity will be presented descriptively by treatment group.

Reported and adjudicated CV AEs will be listed by study participant, and if there are a sufficient number of cases they may be summarized by treatment group.

All SAEs will be listed by study participant. If a sufficient number of SAEs are reported, incidence summaries similar to incidence of TEAEs will be included.

Discontinuations due to AE and TEAEs will be listed by study participant and summarized by treatment group.

#### **10.3.4.2. Vital Signs**

Descriptive statistics for the actual measurements and changes from baseline for systolic and diastolic blood pressure and pulse rate will be presented by treatment arm and visit.

Corresponding figures may be presented.

Vital signs will be analyzed using a similar MMRM-based model.

#### **10.3.4.3. Hypoglycemia Episodes**

The rate and incidence analyses will be analyzed. Details will be provided in the SAP. Statistical analysis will be performed for overall total hypoglycemia, documented symptomatic hypoglycemia and nocturnal hypoglycemia. Listing of hypoglycemic episodes and severe hypoglycemic episodes will be presented by visit for each study participant. If a sufficient number of severe hypoglycemic episodes are reported, then incidence summaries and analysis similar to incidence of hypoglycemic episodes will be included.

